## 2. SCHEDULE OF ACTIVITIES (SOA)

Procedures	Screen	Run-In			Treatment Period						EW	Follow -up	Notes
Visit/Contact	V1	V2	V3	V4	V5	V6	V7	V8	V9	V10		V11	
Month of Study	-1	0	0	0	1	2	3	4	5	6			
Day of Study	-28	0	0	0	28	56	84	112	140	168		175	
Visit Window (days)		±2	±2	±2	±2	±7	±7	±7	±7	±7		±2	
Conditional Visits			X	X		X	X	X	X				
SCREENING ASSESSMENTS													
Written Informed Consent	X												Signed by the subject and HCP/ designee prior to any other study assessments. May be completed at a separate visit to screening if required.
Subject Demography	X												
Medical History	X												
Asthma History	X												Including exacerbation history for previous 12 months and those involving hospitalisation
Therapy History	X												Maintenance therapy over previous 12 months, including number of prescriptions requested or provided
Physical Exam	X												Full physical including height, weight and vital signs
Inclusion/Exclusion Criteria	X	X	X	X									ACT assessment for inclusion required at run-in visits
Randomisation		X	X	X									Subject randomised to treatment at only one of V2, V3 or V4 once ACT criteria is met

Procedures	Screen	Run-In			Treatment Period						EW	Follow -up	Notes
Visit/Contact	V1	V2	V3	V4	V5	V6	V7	V8	V9	V10		V11	Conditional Visits: V3 & V4 are only required if a subject is not included at prior run in visit. V6, V7, V8 & V9 are only required for Treatment arms 1 & 3. Randomisation to treatment arms will occur at Visit 2,3 or 4 when randomisation criteria have been met
Month of Study	-1	0	0	0	1	2	3	4	5	6			
Day of Study	-28	0	0	0	28	56	84	112	140	168		175	
Visit Window (days)		±2	±2	±2	±2	±7	±7	±7	±7	±7		±2	
Conditional Visits			X	X		X	X	X	X				
SAFETY ASSESSMENTS													
Concomitant Medication		X											
Urine Pregnancy Test	X	X	X	X	X					X	X		
SAEs	X					X							
Non-Serious Adverse Events that leads to withdrawal	X					X							Non-serious adverse events that leads to dose modification, drug discontinuation, or withdrawal from the trial. Collected from start of run in
Non-serious Adverse Drug Reactions	X					X							Collected from start of run in
Exacerbations	X					X							Severe Exacerbation are to be reviewed and recorded. Collected from start of run in
Unscheduled HCP visits						X							All secondary care contacts and all primary care contacts related to Asthma
QUESTIONNAIRES & Patient Reported Outcomes (PROs) (Performed in the order given here)													

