### 3.3.2. Overall Benefit: Risk Conclusion

GlaxoSmithKline (GSK) has assessed this study for any potential risks that a subject may experience. The investigational product (IP) FF/VI will be used as is detailed in the prescribing information and has an acceptable safety profile for clinical use and there are no significant associated risks. This conclusion is supported by the results of previously performed clinical studies with the products in healthy volunteers and subjects with Asthma and COPD and post-marketing experience (see local label).

There is a small risk of destabilising asthma when switching to Relvar/Breo. Patients will be provided with rescue medication and will be educated to recognise symptoms of asthma worsening and instructed to contact the HCP in this event.

Taking into account the measures taken to minimize risk to subjects participating in this study, the potential risks identified, associated with FF/VI are justified by the anticipated benefits that may be afforded to patients with asthma.

More detailed information about the known and expected benefits and risks and reasonably expected adverse events of Relvar/Breo ICS/LABA may be found in the IB, Summary of Product Characteristics and Subject Information Leaflet.

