### 11.4.2. Safety Analyses

All safety analyses will be performed on the ITT Population.

Endpoint	Statistical Analysis Methods
Safety	
SAEs, AEs leading to withdrawal and non-serious ADRs will be collected.
 
Safety endpoints will include:
 
 
• Incidence and type of serious adverse events
 
• Incidence and type of adverse drug reactions
 
• Incidence and type of non-serious adverse events leading to study withdrawal
 
• Incidence of subjects experiencing a severe exacerbation
 
 
The incidence of any given adverse event (SAE or ADR) for each treatment group is defined as the proportion of subjects in that group who have experienced at least one such adverse event during the study period.
 
The number and percentage of subjects with SAEs, non-serious ADRs and AEs leading to study withdrawal will be summarised by preferred term.
 
The number and percentage of subjects experiencing severe exacerbations over treatment period and the follow-up period will be summarised for each treatment group alongside the primary causes of the exacerbation.

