## 8. SAFETY ANALYSES

Safety analyses will be based on the ITT Population and will include all study data (run-in, on and post-treatment), unless otherwise specified.

Safety endpoints will include:

- Incidence and type of serious adverse events
- Incidence and type of adverse drug reactions (ADR)
- Incidence and type of non-serious adverse events leading to study withdrawal

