2.15.	ITT	EFF_T1	Summary of Asthma Control Test (ACT) Total Score	Programming Note: Add screening visit score. [1] Baseline ACT total score is taken at Randomisation visit.	SAC [2] DRY RUN [1]
2.16.	ITT	EFF_T4	Summary of the Statistical Analysis of Change from Baseline (Randomisation) in ACT Total Score at Month 6		SAC [2] DRY RUN [1]
2.17.	ITT	EFF_T12	Summary of Percentage of Subjects Who Have Either an ACT Total Score $\geq 20$ and/ or $\geq 3$ Point Increase from Baseline in ACT Total Score	See SLS T2.1	SAC [2] DRY RUN [1]
2.18.	ITT	EFF_T13	Summary of the Statistical Analysis of Percentage of Patients Who Have an ACT Total Score of $\geq 20$ at Month 6		SAC [2] DRY RUN [1]
2.19.	ITT	EFF_T13	Summary of the Statistical Analysis of Percentage of Patients with an Increase from Baseline $\geq 3$ in ACT Total Score at Month 6		SAC [2] DRY RUN [1]
2.20.	ITT	EFF_T13	Summary of the Statistical Analysis of Percentage of Patients Who Have Either an ACT Total Score of $\geq 20$ and/or an Increase from Baseline of $\geq 3$ in ACT Total Score at Month 6		SAC [2] DRY RUN [1]
Unscheduled Health Care Utilisation					
2.21.	ITT	EFF_T14	Summary of Unscheduled Asthma Related Healthcare Utilisation During the Study		SAC [2] DRY RUN [1]
2.22.	ITT	EFF_T22	Summary of Primary Care Visits relating to HCP Dashboard Review		SAC [2] DRY RUN [1]

Efficacy Tables					
No.	Population	IDSL / Example Shell	Title	Programming Notes	Deliverable [Priority]
Severe On-treatment Exacerbations					
2.23.	ITT	EFF_T15	Summary of Severe On-Treatment and Post-Treatment Asthma Exacerbations	Exacerbation duration and rates will only be determined from those events that have dates of onset and resolution  Include a total column	SAC [2] DRY RUN [1]
Asthma Symptom Utility Index (ASUI)					
2.24.	ITT	EFF_T1	Summary of Asthma Symptom Utility Index (ASUI) Score	Programming Note: Add screening visit score. Decimal places need to be increased by 2 dp for all values. [1] Baseline ASUI total score is taken at Randomisation visit.	SAC [2] DRY RUN [1]
2.25.	ITT	EFF_T16	Summary of Statistical Analysis of Percentage of Patients Meeting a Responder Threshold of $\geq 0.09$ Points Improvement (Increase) from Baseline (Randomisation) for the ASUI Total Score at Visit 10 (Month 6)		SAC [2] DRY RUN [1]
2.26.	ITT	EFF_T4	Summary of Statistical Analysis of Change from Baseline (Randomisation) in Asthma Symptom Utility Index (ASUI) Score at Visit 10 (Month 6)		SAC [2] DRY RUN [1]

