### 10.8.10. Non-ICH Listings

Non-ICH: Listings					
No.	Population	IDSL / Example Shell	Title	Programming Notes	Deliverable [Priority]
Study Population					
20.	Enrolled	POP_L1	Listing of Subjects Screened but Not in the Intent-to-Treat Population		SAC [2]
21.	ITT	POP_L2	Listing of Subjects by Country		SAC [2]
22.	ITT	POP_L3	Listing of Family History of Cardiovascular Risk Factors		SAC [2]
23.	ITT	IDSL_SU2	Listing of Substance Use		SAC [2]
24.	ITT	POP_L4	Listing of Asthma History		SAC [2]
25.	ITT	POP_L5	Listing of Prescription Details		SAC [2]
26.	ITT	POP_L6	Listing of Preferred time of dosing		SAC [2]
27.	ITT	POP_L7	Listing of HCP Dashboard Review		SAC [2]
28.	ITT	POP_L8	Listing of Treatment Compliance		SAC [2]
Medical Conditions					
29.	ITT	IDSL_MH2	Listing of Medical Conditions		SAC [2]

Non-ICH: Listings					
No.	Population	IDSL / Example Shell	Title	Programming Notes	Deliverable [Priority]
Concomitant Medications					
30.	ITT	IDSL_CM3	Listing of Concomitant Medications	Note: IDSL shell in development. Required for ClinPharm studies instead of a corresponding table. Not required for studies where a table is produced.	SAC [2]
31.	ITT	IDSL_CM6	Relationship between ATC Level 1, Ingredient and Verbatim Text		SAC [2]
Adverse Events of Special Interest					
32.	ITT	SAFE_L1	Listing of Adverse Event of Special Interest Group, Subgroup, Sub-SMQ and Preferred Term		SAC [2]
Device Malfunction					
33.	Enrolled	SAFE_L2	Listing of Relvar/Breo Ellipta Sensor Status		SAC [2]
34.	Enrolled	SAFE_L3	Listing of Salbutamol MDI Sensor Status		SAC [2]
35.	ITT	SAFE_L4	Listing of Sensor App Status		SAC [2]
36.	ITT	SAFE_L5	Listing of Device Malfunction		SAC [2]

Non-ICH: Listings					
No.	Population	IDSL / Example Shell	Title	Programming Notes	Deliverable [Priority]
Efficacy					
37.	ITT	EFF_L1	Listing of Relvar/Breo ELLIPTA Adherence		SAC [2]
38.	ITT	EFF_L2	Listing of Salbutamol MDI Rescue Free Days and Total Rescue Use		SAC [2]
39.	ITT	EFF_L3	Listing of Patient Reported Outcome Questionnaire Total Scores – ACT, ASUI, MARS-A, PAM-13 and SGRQ		SAC [2]
40.	ITT	EFF_L3	Listing of Patient Reported Outcome Questionnaire Total Scores – BMQ	Replace the different questionnaire headings with the separate scales of the BMQ general and specific	SAC [2]
41.	ITT	EFF_L4	Listing of Severe Asthma Exacerbations		SAC [2]
42.	ITT	EFF_L5	Listing of Unscheduled Asthma Related Healthcare Utilisation		SAC [2]

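### Table 2.23 omits the primary causes of severe exacerbation that Protocol 11.4.2 requires; separately, no SAP table counts severe exacerbations in run-in

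*SAP*

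**What the plan says.** **Protocol.** Section 11.4.2 lists four safety endpoints, one of which is the incidence of subjects with a severe exacerbation. It says that the number and percentage of subjects with "severe exacerbations over treatment period and the follow-up period will be summarised for each treatment group", "alongside the primary causes of the exacerbation". On collection, the Schedule of Activities states: "Severe Exacerbation are to be reviewed and recorded. Collected from start of run in". Section 9.2.6.1 gives two start points in the same section, the start of treatment and signature of the consent form. It also says that an exacerbation is recorded as an AE only if it qualifies as an SAE.

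**SAP.** Section 8 lists three safety endpoints; severe exacerbation is not among them. Its general rule is: "Safety analyses will be based on the ITT Population and will include all study data (run-in, on and post-treatment), unless otherwise specified". Exacerbations are handled in 7.3.2.2 under health care utilisation, with on-treatment events counted from the randomisation date. The planned displays are Table 2.23 (ITT), "Summary of Severe On-Treatment and Post-Treatment Asthma Exacerbations", and Listing 41 (ITT), "Listing of Severe Asthma Exacerbations". Section 10.3.1.2 defines three phases for exacerbations: run-in, on-treatment and post-treatment. SAP Table 1, which records departures from the protocol's analysis plan, is silent on all of this.

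**The concern.** Two separate things are missing.

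The first is promised content. The protocol told its readers that severe exacerbations would be reported with their primary causes as part of safety. The SAP moves the endpoint into the efficacy tables and drops the causes without saying so. A reader of the study report would not know that a planned safety summary had been cut.

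The second is a period. Participants take Relvar/Breo from entry into run-in, and Protocol 3.3.2 acknowledges: "There is a small risk of destabilising asthma when switching to Relvar/Breo". For participants who do switch, run-in is when that risk first applies. The SAP collects severe exacerbations in that period and defines a phase for them, then does not count them. It does plan run-in summaries for AEs and SAEs, including for participants outside ITT, and gives no reason for treating exacerbations differently.

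**Working it through.** **Step 1: primary causes.**

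| Place | Severe exacerbation a safety endpoint? | Primary cause shown? |
|---|---|---|
| Protocol 11.4.2 | Yes | Required, by treatment group |
| SAP section 8 | No | No |
| Table 2.23, shell EFF_T15 | Placed under efficacy | No cause row. Rows: subjects, counts, duration, outcome, corticosteroids, hospitalisation, emergency room visit, intubation, withdrawal, annual rate |
| Listing 41, shell EFF_L4 | Placed under efficacy | No cause column |
| SAP Table 1 | Change not logged | Change not logged |

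No other planned display supplies causes.

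**Step 2: periods in Table 2.23.** Protocol 11.4.2 asks for the treatment and follow-up periods. Protocol 6.4 has a subject enter the treatment period only after completing run-in and meeting the randomisation criteria. EFF_T15 has an on-treatment page and a note to repeat it for post-treatment; on-treatment starts at randomisation (SAP 10.3.1.2). On periods, therefore, Table 2.23 matches the protocol sentence.

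**Step 3: where a run-in severe exacerbation can appear.**

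| Display | Population | What it shows of a run-in event |
|---|---|---|
| Table 2.23 | ITT | Nothing |
| Table 1.29 | ITT | Medications given for it; not a count of events |
| Tables 3.2, 3.14 | ITT | The event, only if it is an SAE |
| Tables 3.3, 3.15 | Not in ITT | The event, only if it is an SAE |
| Tables 3.5, 3.6 (non-serious run-in AEs) | ITT; not in ITT | Nothing, because a non-serious exacerbation is not recorded as an AE |
| Listing 41 | ITT | Possibly listed; neither title nor shell restricts the phase |

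The run-in phase defined in 10.3.1.2 is used by no exacerbation count. For a run-in failure, who is not in ITT, a non-serious severe exacerbation has no exacerbation table or listing.

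**Step 4: how much time is involved.** Inputs: run-in of 1, 2 or 3 months (Protocol 5.1), 28-day months and Day 168 as the end of treatment (Schedule of Activities), treatment period of 6 months.

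- The plan's own figure: 6 + 1, 6 + 2 and 6 + 3 give 7, 8 and 9 months on study, as the protocol synopsis states.
- Run-in share of a completer's planned Relvar/Breo time, for r run-in months, is 28r / (28r + 168).
  - r = 1: 28/196 = 14.3%
  - r = 2: 56/224 = 25.0%
  - r = 3: 84/252 = 33.3%

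This ignores visit windows and the up to 7 days allowed between screening and the start of run-in.

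**The case against.** The strongest defence concerns run-in. Protocol 11.4.2 does not mention it, so a reader who infers that Table 2.23 breaches the protocol by leaving it out is wrong; Step 2 shows that the periods agree. This part of the defence stands in full.

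Next, the rule in SAP section 8 has an exception for cases specified otherwise, and 7.3.2.2 does specify counting from randomisation. Protocol section 4 lists the annualised severe exacerbation rate as an exploratory endpoint on the effect of the CIS, and its safety objective does not name exacerbations. The CIS starts at randomisation, and run-in has a single arm. This stands in part. The run-in gap is an inconsistency within the SAP, not a clear violation of a rule. However, 7.3.2.2 is a health care utilisation analysis, and a protocol safety endpoint reached it only because section 8 dropped it.

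Third, run-in events are not invisible. The protocol's definition of a severe exacerbation turns on systemic corticosteroids or antibiotics, so ITT events should normally leave a trace in Table 1.29. Serious events reach the SAE tables, and Listing 41 may show the rest. That stands, and it rules out saying that run-in events appear nowhere. What is missing is a count, plus any exacerbation display for non-serious events outside ITT.

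Finally, these are descriptive gaps, and no hypothesis test depends on them. That is correct. None of this defence answers the missing causes or the silence of SAP Table 1.

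**Conclusion.** The point holds in two parts of different weight.

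**Causes and endpoint status: firm.** The SAP omits content that Protocol 11.4.2 requires, removes the endpoint from the safety list, and logs neither change. The documents do not show a cause field in the eCRF, so it cannot be assumed that the data exist.

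**Run-in count: a gap in the SAP, not a protocol breach.** No table counts severe exacerbations over 14% to 33% of a completer's planned Relvar/Breo time. That range rests on 28-day months and full completion.

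Several stronger readings are tempting but unsupported:

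- Run-in is not the period after a switch for everyone. Protocol 5.4 says that participants switch only if not already prescribed Relvar/Breo, and the proportion who do is not given.
- The time share cannot be turned into a number of uncounted events. The documents give no expected severe exacerbation rate and no expected distribution of run-in lengths.
- The number of run-in failures cannot be derived. The 600 - 432 = 168 screened but not randomised include screen failures, who never enter run-in.
- Collection of exacerbations before randomisation was not new with Amendment 01. Section 9.2.6.1 of the original protocol already gave consent signature as a start point, beside the start of treatment.

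The primary analysis is unaffected. What is at stake is the completeness of safety reporting.

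**What to change.** 1. Restore severe exacerbation to the safety endpoints in SAP section 8.
2. If cause is captured in the eCRF, add primary-cause rows by arm to EFF_T15 and a cause column to EFF_L4. If it is not captured, log the removal in SAP Table 1 with the reason.
3. Add a run-in panel to Table 2.23 using the phase already defined in 10.3.1.2, total column only, since the period precedes randomisation.
4. Add a matching total-column summary for enrolled participants not in ITT, as Tables 3.3, 3.6 and 3.15 already do for AEs and SAEs.
5. Set the population of Listing 41 to Enrolled.
6. Reconcile the two collection start points in Protocol 9.2.6.1 with each other and with the Schedule of Activities, so that it is clear which run-in events the database should contain.

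The cost is a few extra rows, one small table and a change of listing population, plus a clarification of the protocol text. The run-in items use events that the Schedule of Activities already has sites record; the cause rows depend on what the eCRF holds.

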#### **9.2.6.1. Asthma Exacerbations**

For the purposes of this study, severe asthma exacerbations will be collected and recorded on the asthma exacerbation eCRF page from the start of treatment until follow up/or the EW visit for those subjects that withdraw from participation in the study.

A severe asthma exacerbation is defined as deterioration of asthma requiring the use/additional use of systemic corticosteroids (tablets, suspension, or injection), or antibiotics and inpatient hospitalisation, or emergency department visit due to asthma that required systemic corticosteroids or antibiotics. Further clarification will be present in the SRM.

Asthma exacerbations should not be recorded as an AE unless they meet the definition of an SAE.

These events will be recorded on the DRE page in the subject's eCRF within 24 hours of the physician becoming aware. The time period for collection of exacerbation information in the eCRF will be from the time that the ICF is signed until the Exit visit or EW.

For consistency, exacerbations separated by less than 7 days will be treated as a continuation of the same exacerbation.

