
 
The number and percentage of participants reporting an asthma exacerbation (on-treatment and post-treatment) will be summarised by treatment arm.
 
The number and percentage of participants with each number of exacerbations (0, 1, 2, 3, 4, >4) and the total number of exacerbations per treatment arm will also be summarised.
 
For the purposes of summarizing these data, the annualized rate of severe asthma exacerbations for the ITT population will be calculated for each participant as 
 
the number of exacerbations / time on Relvar/Breo (in years) from randomisation.
 
 
 
The summaries will include on-treatment exacerbations, from randomisation date to min(stop date of exposure + 1 day, date of study discontinuation).
 
The number and percentage of participants with an exacerbation that led to withdrawal of study, hospitalization, systemic/oral corticosteroids/antibiotics/medication being taken, or emergency room visit will be summarised by treatment arm.
 
A listing of severe exacerbations will be provided.
 

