#### 10.3.1.2. Study Phases for Asthma Exacerbations

Study Phase	Definition
Run-in-Treatment	(Exacerbation Onset Date $\geq$ Screening Visit date) and (Exacerbation Onset Date < Randomisation Date)
On-Treatment	(Exacerbation Onset Date $\geq$ Randomisation Date) and (Exacerbation Onset Date $\leq$ Last Treatment Stop Date)+1
Post-Treatment	Exacerbation Onset Date $>$ Last Treatment Stop Date+1

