
Missing onset or resolution dates will be handled as follows:
 
 
Single event with missing onset and/or resolution dates: 
 
(a) Missing onset date: set onset date = study treatment start date
 
(b) Missing resolution date: set resolution date = study treatment stop date
 
(c) Both missing: imputed per both (a) and (b)
 
 
 
Multiple events, one event with some missing onset/resolution dates; on the assumption any partial date information does not occur during the other events: 
 
(a) Missing onset date: set onset date = max[(resolution date of the nearest previous event) + 1 day, study treatment start date]
 
(b) Missing resolution date: set resolution date = min[(onset date of the nearest subsequent event) - 1 day, study treatment stop date]
 
(c) Both missing: determine the largest gap between study treatment start date and first event onset date, between first event resolution date and next event(s) onset dates (if any), between last event resolution date and study treatment stop date. If there is more than one gap which is the largest, then take the first occurrence. Then impute as follows:  <math display="block">\text{onset date} = (\text{onset date of largest gap}) + 1 \text{ day}</math> <math display="block">\text{resolution date} = (\text{resolution date of largest gap}) + 1 \text{ day}</math> 
 
 
 

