	>3	xxx (%)				
	Total [1]	xxx	xxx	xxx	xxx	xxx

[1] Total number of days/ contacts across all subjects.

Example : EFF\_T14  
 Protocol : 207040  
 Population : Intent-to-Treat

Page 3 of x

Table 2.xx  
 Summary of Unscheduled Asthma Related Healthcare Resource Utilisation During the Study

		Arm 1 (N=XXX)	Arm 2 (N=XXX)	Arm 3 (N=XXX)	Arm 4 (N=XXX)	Arm 5 (N=XXX)
Number of emergency room visits	n	xxx	xxx	xxx	xxx	xxx
	0	xxx (%)				
	1	xxx (%)				
	2	xxx (%)				
	3	xxx (%)				
	>3	xxx (%)				
	Total [1]	xxx	xxx	xxx	xxx	xxx
Number of days inpatient hospitalisation days	n	xxx	xxx	xxx	xxx	xxx
	0	xxx (%)				
	1	xxx (%)				
	2	xxx (%)				
	3	xxx (%)				
	>3	xxx (%)				
	Total [1]	xxx	xxx	xxx	xxx	xxx

[1] Total number of days/ contacts across all subjects.

Example : EFF\_T22  
Protocol : 207040  
Population : Intent-to-Treat

Page 1 of x

Table 2.xx  
Summary of Primary Care Visits relating to HCP Dashboard Review

	Arm 1 (N=XXX)	Arm 2 (N=XXX)	Arm 3 (N=XXX)	Arm 4 (N=XXX)	Arm 5 (N=XXX)
Number of Subjects called in for an unscheduled clinic visit	xx	xx	xx	xx	xx
Number of unscheduled clinic visits	xx	xx	xx	xx	xx

Example : EFF\_T15

Protocol : 207040

Population : Intent-to-Treat

Page 1 of 2

Table 2.xx  
Summary of Severe On-Treatment and Post-Treatment Asthma Exacerbations

Time: On-Treatment

	Arm 1 (N=xxx)	Arm 2 (N=xxx)	Arm 3 (N=xxx)	Arm 4 (N=xxx)	Arm 5 (N=xxx)	Total (N=xxx)
No. of subjects with one or more severe asthma exacerbation	xx (xx%)					
Total no. of severe asthma exacerbations	xx	xx	xx	xx	xx	xx
Number of severe asthma exacerbations per subject						
0	xx (xx%)					
1	xx (xx%)					
> 1	xx (xx%)					
Duration of severe asthma exacerbation (days) [1]						
n	xx	xx	xx	xx	xx	xx
Mean	xx.X	xx.X	xx.X	xx.X	xx.X	xx.X
SD	x.xx	x.xx	x.xx	x.xx	x.xx	x.xx
Median	xx.X	xx.X	xx.X	xx.X	xx.X	xx.X
Min.	xx	xx	xx	xx	xx	xx
Max.	xx	xx	xx	xx	xx	xx

[1] Summary only includes exacerbations for which a date of onset and resolution were provided in the eCRF.

Programming Note: Repeat for Post-Treatment

Example : EFF\_T15

Protocol : 207040

Population : Intent-to-Treat

Page 2 of 2

Time: On-Treatment

Table 2.xx  
Summary of Severe On-Treatment and Post-Treatment Asthma Exacerbations

	Arm 1 (N=xxx)	Arm 2 (N=xxx)	Arm 3 (N=xxx)	Arm 4 (N=xxx)	Arm 5 (N=xxx)	Total (N=xxx)
No. of subjects with an exacerbation outcome						
Resolved	xx (xx%)					
Fatal	xx (xx%)					
Not resolved	xx (xx%)					
No. of subjects with exacerbations:						

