Requiring use of systemic/oral corticosteroids	xx (xx%)					
Leading to hospitalisation	xx (xx%)					
Requiring emergency room visit	xx (xx%)					
No. of subjects with exacerbations requiring intubation	xx (xx%)					
No. of subjects with exacerbations leading to withdrawal from study	xx (xx%)					
Annual severe asthma exacerbation rate [1]						
n	XX	XX	XX	XX	XX	XX
Mean	XX.X	XX.X	XX.X	XX.X	XX.X	XX.X
SD	X.XX	X.XX	X.XX	X.XX	X.XX	X.XX
Median	XX.X	XX.X	XX.X	XX.X	XX.X	XX.X
Min.	XX	XX	XX	XX	XX	XX
Max.	XX	XX	XX	XX	XX	XX

[1] Summary only includes exacerbations for which a date of onset and resolution were provided in the eCRF..

Example EFF\_T1  
 Protocol : 207040  
 Population : Intent-to-Treat

Page 1 of 1

Table 2.xx  
 Summary of Asthma Symptom Utility Index (ASUI) Score

Visit		Arm 1 (N=xxx)	Arm 2 (N=xxx)	Arm 3 (N=xxx)	Arm 4 (N=xxx)	Arm 5 (N=xxx)
Baseline [1]	n	XX	XX	XX	XX	XX
	Mean	XX.X	XX.X	XX.X	XX.X	XX.X
	SD	X.XX	X.XX	X.XX	X.XX	X.XX
	Median	XX.X	XX.X	XX.X	XX.X	XX.X
	Min.	XX	XX	XX	XX	XX
	Max.	XX	XX	XX	XX	XX
Visit 5 (Month 1)	n	XX	XX	XX	XX	XX
	Mean	XX.X	XX.X	XX.X	XX.X	XX.X
	SD	X.XX	X.XX	X.XX	X.XX	X.XX
	Median	XX.X	XX.X	XX.X	XX.X	XX.X
	Min.	XX	XX	XX	XX	XX
	Max.	XX	XX	XX	XX	XX
Change from Baseline at Visit 5 (Month 1)	n	XX	XX	XX	XX	XX
	Mean	XX.X	XX.X	XX.X	XX.X	XX.X
	SD	X.XX	X.XX	X.XX	X.XX	X.XX
	Median	XX.X	XX.X	XX.X	XX.X	XX.X
	Min.	XX	XX	XX	XX	XX
	Max.	XX	XX	XX	XX	XX

[1] Baseline ASUI total score is taken at randomisation visit.

Programming note: repeat, Visit 10 (Month 6), Change from Baseline at Visit 10 (Month 6), Early Withdrawal

Example EFF\_T16

Protocol : 207040

Population : Intent-to-Treat

Page 1 of 1

Table 2.xx

Summary of Statistical Analysis of Percentage of Subjects Meeting a Responder Threshold of 0.09 Points Improvement (Increase) from Baseline (Randomisation) for the ASUI Total Score at Visit 10 (Month 6)

	Arm 1 (N=xxx)	Arm 2 (N=xxx)	Arm 3 (N=xxx)	Arm 4 (N=xxx)	Arm 5 (N=xxx)
n	xxx	xxx	xxx	xxx	xxx
Responder [1]	xxx (xx%)				
Non-Responder	xxx (xx%)				
CIS Arm v Arm 5					
Adjusted Odds Ratio	x.xx	x.xx	x.xx	x.xx	
95% C.I.	(x.xx, x.xx)	(x.xx, x.xx)	(x.xx, x.xx)	(x.xx, x.xx)	
p-value	x.xx	x.xx	x.xx	x.xx	

[1] Responder is defined as an ASUI total score  $\geq 0.09$  points increase from baseline.

Note: The analysis method was logistic regression adjusted for randomised treatment arm, baseline ASUI total score, country, gender and age

Example : EFF\_T4

Protocol : 207040

Population: Intent-to-Treat

Page 1 of 1

Table 2.xx

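### Table 2.23 restricts the exploratory severe-exacerbation rate to events with both onset and resolution dates, in conflict with the SAP's own rate definition and date-imputation rule

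*SAP*

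**What the plan says.** SAP 7.3.2.2 defines each participant's annualised rate as "the number of exacerbations / time on Relvar/Breo (in years) from randomisation". It names the events that count: "The summaries will include on-treatment exacerbations, from randomisation date to min(stop date of exposure + 1 day, date of study discontinuation". It sets no condition on resolution. SAP 10.3.1.2 classifies an exacerbation as run-in, on-treatment or post-treatment from its onset date. SAP 10.5.2 computes years exposed from the randomisation date and the last treatment stop date.

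The display specification adds a condition. The programming note to Table 2.23 in SAP 10.8.6 reads "Exacerbation duration and rates will only be determined from those events that have dates of onset and resolution". In mock shell EFF_T15 (SAP Appendix 9), footnote [1] on the annual rate row reads "Summary only includes exacerbations for which a date of onset and resolution were provided in the eCRF". The duration row of the same shell carries the same footnote. The row "Total no. of severe asthma exacerbations" carries none, and the outcome rows include one for events that have not resolved.

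Two further SAP sections deal with missing exacerbation dates. For a single event, SAP 10.5.3.3 has the rule "b) Missing resolution date: set resolution date = study treatment stop date", and a missing onset date becomes the treatment start date. SAP 10.6.3 says exacerbations are handled as adverse events are. There, completely missing dates stay missing, and an event without an onset date is taken as on-treatment.

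Protocol 9.2.6.1 collects severe exacerbations "from the start of treatment until follow up/or the EW visit for those subjects that withdraw from participation in the study", and treats exacerbations less than 7 days apart as one continuing event.

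**The concern.** Duration needs two dates. Under SAP 7.3.2.2 the rate is a count over exposure time, and neither part uses the resolution date. Carrying the two-date condition over to the rate removes an event that happened on treatment without removing the time at risk, so any error is downward. One table could then show a total number of events and a rate built from fewer events.

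Open events are foreseeable. The shell has an outcome row for them, collection stops at follow-up or the early withdrawal visit, and follow-up is one week after Visit 10 (Protocol 5.1). Protocol 9.2.3 states follow-up to resolution or stabilisation for SAEs, but exacerbations that are not SAEs are not recorded as adverse events. A participant who withdraws during an exacerbation may therefore have no resolution date, and that event would be left out of the rate. If such events are spread unevenly over the arms, the comparison with Arm 5 shifts as well.

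**Working it through.** The documents state no exacerbation rate, event count or power for this endpoint, so there is no planned figure to reproduce. The check has two parts.

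**Rules side by side**

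| Item | Place | Uses resolution date? |
|---|---|---|
| Rate definition | SAP 7.3.2.2 | No |
| On-treatment status | SAP 10.3.1.2 | No |
| Years exposed | SAP 10.5.2 | No |
| Total-events row | Shell EFF_T15 | No |
| Rate, programming note | SAP 10.8.6, Table 2.23 | Yes |
| Rate row, footnote [1] | Shell EFF_T15 | Yes, from the eCRF |
| Missing resolution date | SAP 10.5.3.3 | Imputed |
| Missing resolution date | SAP 10.6.3 | Left missing |

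**Size**

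Inputs: 168 days of treatment (schedule of activities) and 432/5 = 86.4 randomised per arm, taken as 86. Event counts, stopping days, event durations and the share of undated events are assumptions.

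1. Full follow-up is 168/365.25 = 0.460 years. One event gives 1/0.460 = 2.174 per year. If it is undated, the participant contributes 0 instead.
2. In the arm mean, one such event is worth 2.174/86 = 0.025 per year. With 5, 10 or 20 events, all in participants with full follow-up, the mean is 0.126, 0.253 or 0.506. Without one event it is 0.101, 0.228 or 0.480, which is 20%, 10% or 5% lower.
3. An early stopper weighs more in a mean of individual rates. Suppose 1 of 10 events is undated and belongs to a participant who stopped early:

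| Stop day | Individual rate (365.25/day) | Divided by 86 | Arm mean, all events | Mean after the drop | Loss |
|---|---|---|---|---|---|
| 140 | 2.61 | 0.030 | 0.258 | 0.228 | 12% |
| 84 | 4.35 | 0.051 | 0.278 | 0.228 | 18% |
| 28 | 13.04 | 0.152 | 0.379 | 0.228 | 40% |

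The day-28 row is a corner case.

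4. If a share q of events is undated and follow-up is equal, the reported rate is the true rate times (1 − q). The ratio of Arm 1 to Arm 5 is multiplied by (1 − q1)/(1 − q5). Equal shares leave it unchanged. Shares of 5% and 10% turn a true ratio of 1 into 0.95/0.90 = 1.056, and 0% and 10% give 1/0.90 = 1.111.
5. How many events might be open at Visit 11? With uniform onset over 169 days (168 plus the one-day allowance) and an assumed duration of d days, the share is (d − 7)/169. That is 0% for 7 days, 7/169 = 4.1% for 14 days and 14/169 = 8.3% for 21 days.

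**The case against.** The strongest objection is SAP 10.5.3.3. Once its imputation has been applied, every event has both dates, and the note to Table 2.23, which does not mention the eCRF, then excludes nothing. A reader might infer that the SAP plainly drops every event without a resolution date. The documents do not support that. The exclusion depends on the eCRF wording in the shell footnote, or on the no-imputation rule in SAP 10.6.3, taking precedence over SAP 10.5.3.3. What stands is a conflict: two programmers following different sections would report different rates.

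A reader might also infer that a rate never needs a resolution date. Under the 7-day rule in Protocol 9.2.6.1 it can: the gap between two events is judged from the end of the first. Counting every record whatever its dates could count one continuing episode twice. This does not justify dropping a single or last open event, which is at least one event.

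The practical case for leaving the text alone also has weight. The endpoint is descriptive, the footnote discloses the restriction, and all events stay in the counts and in the listing of severe exacerbations. The rationale for Protocol Amendment 01 reports much lower dropout than expected, so few events should be open at an early withdrawal visit. Exacerbations that meet the SAE definition are followed further. This limits the likely size, but it does not make the sections agree.

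**Conclusion.** The point holds as an inconsistency with a known direction. The note to Table 2.23 and the rate-row footnote disagree with the rate definition, the onset-based phase rule, the unfiltered rows of the same table and the imputation rule in SAP 10.5.3.3, which itself disagrees with SAP 10.6.3. If the note and footnote are followed, the rate can be biased downward only.

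The size is unknown, because the documents give neither an event rate nor the share of undated events. Under the assumptions shown, one lost event in a participant with full follow-up costs 0.025 per year, or 5% to 20% of an arm's rate with 20 down to 5 events. The effect is zero if all events are dated and is probably small otherwise. The 40% figure should not be read as typical: it needs 1 of 10 assumed events to be undated and to belong to a participant who stopped on day 28.

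No primary or secondary conclusion is touched. Nor does the point show that the planned mean of individual rates is the wrong estimator; that choice is separate from missing dates.

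**What to change.** - In the programming note to Table 2.23, strike the reference to rates, so that the two-date condition governs duration only. In shell EFF_T15, remove footnote [1] from the annual rate row and keep it on the duration row.
- State in SAP 7.3.2.2 that every on-treatment severe exacerbation counts in the rate after the 7-day continuation rule of Protocol 9.2.6.1 has been applied. Say how an undated event followed by another is handled, so that one episode is not counted twice.
- Reconcile SAP 10.5.3.3 and 10.6.3 to a single missing-date rule for exacerbations. It should also cover a missing onset date, which one section imputes and the other leaves missing while calling the event on-treatment.

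The cost is SAP and shell wording, settled before unblinding. No new data are needed and no other analysis changes.
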